6.24. Observation for Drug Induced Liver Injury (DILI)

Throughout the study, all TEAEs, clinical assessments, and clinical laboratory parameters will be closely monitored against the criteria for drug-induced liver injury as detailed in this protocol.

6.24.1. Subjects with Normal Liver Transaminases and Bilirubin at Baseline

Drug-induced liver injury monitoring in subjects with normal liver transaminases and bilirubin at baseline should be performed throughout the study according to the procedures summarized below.

- If subjects with normal baseline liver indices develop elevations of >5 × ULN during the study, repeat testing should be performed within 2 5 days from receipt of results. For Cohort C subjects, repeat testing should be performed within 48 to 72 hours from receipt of results.
 - If there are persistent elevations (ALT > $5 \times ULN$ or TBL > $2 \times ULN$) upon repeat testing, close observation (testing and physical examination 2 to 3 times per week) should be implemented. An important purpose of the close observation is to gather additional clinical information to seek other possible causes of the observed liver test abnormalities, such as one of the following: acute viral hepatitis, alcoholic and autoimmune hepatitis, hepatobiliary disorders, cardiovascular causes, or concomitant treatments. Discontinuation of study drug should be considered.
- Study drug should be discontinued, and the subject should be followed until resolution of signs or symptoms, in the following situations:
 - \circ ALT >8 × ULN
 - ALT $>5 \times$ ULN and (TBL $>2 \times$ ULN)
 - \circ ALT >5 × ULN with the appearance of fatigue, nausea, vomiting, right upper quadrant pain or tenderness, fever, rash, and/or eosinophilia (> 5%)

For any subjects who present with a constellation of syndromes indicative of liver disease as per the Investigator's overall assessment (i.e., fatigue, nausea, vomiting, right upper quadrant pain or tenderness, fever, rash, and/or eosinophilia [> 5%]), perform liver function tests to determine if liver disease is worsening.

Re-initiation of study drug may be considered after consultation with the Medical Monitor.

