6.21. Adverse Events

An AE is any unfavorable and unintended sign (including an abnormal laboratory finding), symptom, or disease temporally associated with the use of a study drug, whether or not related to the study drug. AEs may also include pre- or post-treatment complications that occur as a result of protocol specified procedures, lack of efficacy, overdose, drug abuse/misuse reports, or occupational exposure. Pre-existing events that increase in severity or change in nature during or as a consequence of participation in the clinical study will also be considered AEs. AEs that occur after the first dose of EFX or during the study treatment and safety follow up periods will be documented on the AE eCRF. The Investigator will assess the AE severity and relationship of the AE to study drug. The Investigator will treat the subject as medically required.

Laboratory values that are outside the laboratory reference range should be reported as AEs only if considered clinically significant by the Investigator.

From the time of obtaining informed consent until 30 days after the last administration of study drug, all SAEs and non-serious AEs related to protocol-mandated procedures will be recorded on the SAE/AE eCRF. All other untoward medical occurrences observed during screening, including exacerbation or changes in medical history, will be captured on the medical history eCRF. Details on recording and reporting AEs are provided below.

Clinical judgment of the Investigator should be used to determine whether a subject is to be withdrawn due to an AE. In the event the subject requests to withdraw from study-related

treatment or the study due to an AE, the subject should be followed for the safety follow up period as outlined in the Schedule of Assessments.

All subjects experiencing AEs, including clinically significant abnormal laboratory values, whether or not associated with use of the study drug, must be monitored until the condition returns to normal, returns to the subject's baseline, until the Investigator determines the AE has reached a stable outcome and is no longer clinically significant, or the subject is considered lost to follow up.

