6.21.2. Relationship

The Investigator or qualified sub-Investigator is responsible for assessing the relationship to study drug using clinical judgment and the following considerations:

- Not related: all AEs should be considered related unless the AE is clearly unrelated to study drug or clearly due to the subject's underlying disease. For a SAE, an alternative causality must be provided (e.g., preexisting condition, underlying disease, intercurrent illness, or concomitant medication).
- Related: There is reasonable possibility that the event may have been caused by the study drug.

Ineffective treatment should not be reported as an AE.

The relationship to study-related procedures (e.g., invasive procedures such as venipuncture or biopsy) should be assessed using the following considerations:

- Not related: Evidence exists that the AE has an etiology other than the study procedure.
- Related: The AE occurred as a result of study procedures.

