6.24.2. Subjects with Elevations in Liver Transaminases or Bilirubin at Baseline

Drug-induced liver injury monitoring in subjects with elevations in liver transaminases or bilirubin at baseline should be performed throughout the study according to the procedures summarized below.

• If subjects with abnormal baseline liver indices develop elevations of ALT >3 × baseline or 300 U/L (whichever occurs first) during the study, repeat testing should be performed within 2 - 5 days.

- If there are persistent elevations (ALT >3 × baseline, or 300 U/L) upon repeat testing, then close observation (testing and physical examination 2 to 3 times per week) should be implemented and discontinuation of study drug should be considered.
- Discontinue the study drug if any of the following occur:
 - \circ ALT increases to >5 × baseline measurements or 400 U/L (whichever occurs first).
 - ALT increase $>3 \times$ baseline measurements or 300 U/L (whichever occurs first) AND the increase is accompanied by a concomitant increase in TBL to $> 2 \times$ ULN.
 - ALT increase >3 × baseline measurements or 300 U/L (whichever occurs first) with the appearance of fatigue, nausea, vomiting, right upper quadrant pain or tenderness, fever, rash, and/or eosinophilia (> 5%)

For any subjects who present with a constellation of syndromes indicative of liver disease as per the Investigator's overall assessment (i.e., fatigue, nausea, vomiting, right upper quadrant pain or tenderness, fever, rash, and/or eosinophilia [> 5%]), perform liver function tests to determine if liver disease is worsening.

Re-initiation of study drug may be considered after consultation with the Medical Monitor.

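### The first liver-retest trigger in Protocol 6.24.1 omits the bilirubin threshold that its own next step uses, and the faster Cohort C recheck is missing from 6.24.2

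*Protocol*

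**What the plan says.** Protocol 6.24.1 covers subjects whose transaminases and bilirubin are normal at baseline. Its first step reads: "If subjects with normal baseline liver indices develop elevations of >5 × ULN during the study, repeat testing should be performed within" 2 to 5 days from receipt of results. It then adds: "For Cohort C subjects, repeat testing should be performed within 48 to 72 hours from receipt of results". The sub-step below it concerns persistent elevations, defined as ALT above 5 × ULN or TBL above 2 × ULN; if these are found "upon repeat testing, close observation (testing and physical examination 2 to 3 times per week) should be implemented". All three discontinuation rules in 6.24.1 require ALT above 5 × ULN or higher. A closing paragraph tells sites that, when a set of liver symptoms appears, they should "perform liver function tests to determine if liver disease is worsening".

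Protocol 6.24.2 covers subjects with raised transaminases or bilirubin at baseline. Its retest rule is ALT above 3 × "baseline or 300 U/L (whichever occurs first) during the study, repeat testing should be performed within 2 - 5 days". It does not say when that interval starts and has no sentence for Cohort C. One of its stop rules is the same ALT rise "AND the increase is accompanied by a concomitant increase in TBL to" above 2 × ULN.

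Protocol 6.24.3 sets close-observation measures within 72 hours for any subject once drug-induced liver injury is suspected.

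**The concern.** In 6.24.1 the entry step and the step after it do not use the same criteria. TBL above 2 × ULN matters on the repeat sample, but nothing in the entry step calls for a repeat at that level. The word *persistent* lets a site infer that TBL above 2 × ULN was meant to start the pathway, while the printed trigger lets another site conclude that it was not. Two sites could handle the same laboratory report differently.

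The stake is delay in following a combined rise in ALT and bilirubin while weekly dosing continues. Section 6.19 also makes the 6.24 criteria grounds for stopping drug and for a causality review by the Data Monitoring Committee (DMC), so the way into that pathway should be unambiguous.

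The second defect is one of placement. The shorter recheck was written for cirrhotic subjects, yet it reaches only those with normal baseline tests. Safety and tolerability is the primary objective of Cohort C.

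**Working it through.** There is no stated figure to reproduce. The check compares the rules with each other and with the visit schedule.

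**1. The literal gap in 6.24.1.** Let A = ALT/ULN and B = TBL/ULN, with all other liver tests at or below 5 × ULN.

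- Retest: A > 5 or B > 5.
- Next step: A > 5 or B > 2.
- Stop on laboratory values alone: A > 8, or A > 5 with B > 2. The third stop rule also needs A > 5, plus symptoms or eosinophilia.

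The next step is met without a retest trigger when A ≤ 5 and 2 < B ≤ 5. On a grid of A and B from 0.5 to 10 in steps of 0.1, this region has 46 values of A (0.5 to 5.0) times 30 values of B (2.1 to 5.0) = 1,380 points. None meets a stop rule. With the trigger rewritten as A > 5 or B > 2, the count is 0. The grid confirms the logic; it says nothing about how often such values occur.

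**2. What covers the gap elsewhere.** The SAP 3.5.2 grading table is CTCAE Version 5.0, which the protocol uses for all subjects. With a normal baseline, ALT above 3 to 5 × ULN is Grade 2, TBL above 1.5 to 3 × ULN is Grade 2, and TBL above 3 to 10 × ULN is Grade 3.

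- *TBL above 2 to 3 × ULN, ALT at most 5 × ULN:* Grade 2 at most. Section 6.23 leaves dosing to the Investigator and asks for no repeat. This is the clearest uncovered band.
- *TBL above 3 to 5 × ULN:* Grade 3. Section 6.23 refers to confirmation by repeat testing and withholding drug if related, and 6.21.2 makes relatedness the default ("all AEs should be considered related unless the AE is clearly unrelated to study drug"). That route gives no retest window and depends on a judgment of clinical significance; section 6.21 says "Laboratory values that are outside the laboratory reference range should be reported as AEs only if considered clinically significant by the Investigator".
- *Other routes:* extra procedures (section 6), additional safety tests (6.13.1) and 6.24.3 are discretionary or need suspicion of liver injury. The last paragraph of 6.24.1 needs symptoms. The opening of 6.24 requires close monitoring, but against these same criteria.

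**3. Wait to the next scheduled liver panel.** Appendices A and B place full chemistry at Baseline and Weeks 1, 4, 8, 12, 16 and 20. Weekly visits between are glucose-only, and the 48–96 hour post-dose visits have no chemistry. Target days are in SAP 3.1.2; windows are ±3 days, so a gap can change by 3 + 3 = 6 days either way. Dosing is on Day 1 and Weeks 1 to 15, after sampling. Doses are counted on the assumption that each result is known before the next weekly dose.

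| Rise seen at | Days to next panel | With windows | Doses before a new result |
|---|---|---|---|
| Week 1 | 29 − 8 = 21 | 15 to 27 | Weeks 2, 3, 4 = 3 |
| Week 4 | 57 − 29 = 28 | 22 to 34 | Weeks 5, 6, 7, 8 = 4 |
| Week 8 | 85 − 57 = 28 | 22 to 34 | Weeks 9, 10, 11, 12 = 4 |
| Week 12 | 113 − 85 = 28 | 22 to 34 | Weeks 13, 14, 15 = 3 |

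An example inside the gap is ALT 4.5 × ULN with TBL 2.9 × ULN and no symptoms.

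**4. Cohort C recheck.** Section 4.2 admits Cohort C subjects with ALT and AST below 5 × ULN, so 6.24.2 applies to some of them. The outer limit is 72 hours in 6.24.1 and 5 × 24 = 120 hours in 6.24.2. The difference is 120 − 72 = 48 hours if both intervals start at receipt of results. The windows overlap from 48 to 72 hours.

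**The case against.** The best counter-argument is that 6.24.1 largely explains itself. A value can persist only if it was raised before, so the sub-step supplies the missing bilirubin threshold, and the opening of 6.24 tells sites to monitor against the printed criteria, which include TBL above 2 × ULN. Alternatively, the two thresholds are deliberate: a large rise prompts a repeat, and either analyte can then escalate. These are both reasonable readings, which is the difficulty: they lead to different actions on the same result.

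A second argument is that harm needs several failures together: a narrow reading, an Investigator who does not suspect liver injury, no repeat ordered and no symptoms. Doses are given in clinic each week with adverse events collected, clinically significant laboratory values must be followed (6.21), the Investigator may stop drug at any time (6.25), and the DMC receives reports of potential liver injury (7.11). This stands, and it makes the wait in the table a worst case. None of these safeguards is a numeric rule.

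Third, a similar pattern escapes 6.24.2: baseline ALT 2 × ULN rising to 4.5 × ULN is 2.25 × baseline and, if below 300 U/L, triggers nothing even with TBL 2.9 × ULN. That is true, but 6.24.2 is gated on ALT throughout and so is internally consistent; whether to add bilirubin there is a clinical choice.

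On the Cohort C recheck, the objection that the effect is trivial is nearly right. A site can retest at 48 to 72 hours and comply with both sections. Where baseline ALT is between 1 and 1.67 × ULN (5 ÷ 3), the 6.24.2 trigger fires below 5 × ULN, so a slightly longer interval could be defended. The documents do not say whether the omission was intended.

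**Conclusion.** Both points hold and should be corrected.

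In 6.24.1, the literal text gives no numeric retest trigger for a normal-baseline subject with TBL above 2 and up to 5 × ULN and no liver test above 5 × ULN. The part with least cover elsewhere is TBL above 2 to 3 × ULN. The worst case is the four-week wait with up to four further doses shown in the table; it assumes a literal reading and no action on judgment or symptoms. The documents do not allow an estimate of how many subjects would fall in this band.

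The Cohort C omission is minor. Stop rules in 6.24.2 already cover the ALT rise combined with raised bilirubin or symptoms, so the longer recheck mainly touches asymptomatic ALT rises without TBL above 2 × ULN.

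Neither point bears on bias, power or type I error. The case for acting is patient safety and uniform conduct across sites.

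**What to change.** In 6.24.1, word the first trigger as ALT (or AST, if the sponsor intends it) above 5 × ULN or TBL above 2 × ULN, to match the sub-step. State the 48 to 72 hour recheck once, for every Cohort C subject whichever section applies, and specify in 6.24.2 that the 2 to 5 day interval runs from receipt of results. No bilirubin-only trigger is proposed for 6.24.2; that is for the sponsor's hepatology advisers.

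The cost is two wording changes in a protocol amendment. Under 8.2.1 this needs documented ethics approval before implementation, at approximately 30 sites (3.2), and it can be bundled with another amendment. Expect a few additional or earlier repeat liver panels, with no new scheduled visits and no more subjects.

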6.19. Criteria for Discontinuation of Study Drug

Study drug must be discontinued in the following instances:

- Liver transplantation
- Subject develops an SAE consisting of a serious hypersensitivity reaction to study drug
- Subject experiences diarrhea that meets the criteria in Section 6.23 for discontinuation.
- Subject experiences a Grade IV Common Terminology Criteria for Adverse Events (CTCAE) or meets the criteria for Drug Induced Liver Injury described in Section 6.24.
 - The Data Monitoring Committee (DMC) should perform a causality assessment. The study drug may be restarted if the DMC concludes that the AE or laboratory abnormalities were not related to study drug, the AE has resolved, laboratory abnormalities have returned to baseline, and the subject is amenable to close clinical follow-up.
 - If, after re-challenge, a subject has a second serious AE or recurrent elevations (even mild or minimal) of total bilirubin, ALT, or AST as defined in Section 6.24.3, study drug should be discontinued permanently.
- Intercurrent illness that would, in the judgment of the Investigator, affect assessments of clinical status to a significant degree. Following resolution of intercurrent illness, the subject may resume study dosing at the discretion of the Investigator, in consultation with the Medical Monitor
- Unacceptable toxicity or toxicity that, in the judgment of the Investigator, compromises the ability to continue study-specific procedures or is considered to not be in the subject's best interest
- Subject or Investigator request to discontinue for any reason
- Significant subject noncompliance
- Significant protocol violation that impacts subject safety

- Pregnancy during the study; refer to Appendix C.
- Discontinuation of the study at the request of Akero, a regulatory agency, or an IRB/IEC/EC.

Cohort C

In addition to the above criteria, study drug must be discontinued in the following instances in Cohort C:

- Development of any decompensation events including ascites, hepatic encephalopathy (HE), or variceal bleeding
- Progression to Child Pugh Class C

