- For a Grade 3 clinical event, or clinically significant laboratory abnormality confirmed by repeat testing, that is considered to be related to investigational medicinal product, investigational medicinal product should be withheld until the toxicity returns to ≤ Grade 2.
- If a laboratory abnormality recurs to ≥ Grade 3 following re-challenge with investigational medicinal product and is considered related to investigational medicinal product, then investigational medicinal product should be permanently discontinued, and the subject managed according to local practice. Recurrence of laboratory abnormalities considered unrelated to investigational medicinal product may not require permanent discontinuation.

Grade 4 Laboratory Abnormality or Clinical Event

- For a Grade 4 clinical event or clinically significant Grade 4 laboratory abnormality confirmed by repeat testing, the DMC should perform a causality assessment. The study drug may be restarted if the DMC concludes that the AE or laboratory abnormalities were not related to study drug, the AE has resolved, laboratory abnormalities have returned to baseline, and the subject is amenable to close clinical follow-up.
- If a laboratory abnormality recurs to ≥ Grade 4 following re-challenge with investigational medicinal product and is considered related to investigational medicinal product, then investigational medicinal product should be permanently discontinued, and the subject managed according to local practice. Recurrence of laboratory abnormalities considered unrelated to investigational medicinal product may not require permanent discontinuation.
- If, after re-challenge, a subject has a second serious AE or recurrent elevations (even mild or minimal) of total bilirubin, ALT, or AST as defined in Section 6.19, study drug should be discontinued permanently.

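### Section 6.24 allows restart after a liver-injury stop without pointing to the DMC conditions in Section 6.19, and the definition cited for recurrent elevations does not exist

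*Protocol*

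**What the plan says.** Section 6.19 lists the situations in which study drug has to stop. One is a Grade IV event; the same bullet adds a subject who "meets the criteria for Drug Induced Liver Injury described in Section 6.24". Under that bullet, "The Data Monitoring Committee (DMC) should perform a causality assessment", and then: "The study drug may be restarted if the DMC concludes that the AE or laboratory abnormalities were not related to study drug", provided also that the event has resolved, laboratory values are back at baseline and the subject is amenable to close follow-up.

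Sections 6.24.1 (normal baseline) and 6.24.2 (raised baseline) set the liver monitoring and stopping thresholds. Each closes with the same sentence on restart: "Re-initiation of study drug may be considered after consultation with the Medical Monitor". Section 6.22 says that DILI is monitored and managed under Section 6.24 and names no other section.

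The rule for a second event after re-challenge appears twice. In 6.19 it covers recurrent elevations of bilirubin, ALT or AST, even slight ones, "as defined in Section 6.24.3, study drug should be discontinued permanently". In 6.23, under Grade 4 events, the same rule reads "as defined in Section 6.19, study drug should be discontinued permanently".

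On retesting, 6.24.1 adds a provision: "For Cohort C subjects, repeat testing should be performed within 48 to 72 hours from receipt of results". Section 6.24.2 has no Cohort C provision and says "repeat testing should be performed within 2 - 5 days".

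**The concern.** These passages govern re-exposure after a suspected liver injury, including in Cohort C, where every subject has compensated cirrhosis and safety is the primary objective. An investigator whose subject crosses a stopping threshold will open Section 6.24, because 6.22 sends DILI management there. The only restart step in that section is a consultation with the Medical Monitor. Nothing in it says that 6.19 also requires a DMC conclusion and three recovery or follow-up conditions. Two sites could handle the same event differently, and each could point to protocol text in support.

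The permanent-stop rule has a different problem. It depends on a definition of recurrent elevation that the reader is sent to find. Subjects with raised ALT or AST at entry are eligible (the screening limit is 5 × ULN in both parts of the study), so it matters whether a recurrent elevation is judged against the ULN, the subject's own baseline or something else.

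**Working it through.** No arithmetic is involved apart from one conversion of hours to days. The check sets the passages side by side and follows each cross-reference to its target.

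**Step 1: restart conditions.**

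| Condition for restart | Section 6.19 | Sections 6.24.1 and 6.24.2 |
|---|---|---|
| DMC concludes event not related | yes | not mentioned |
| Event resolved | yes | not mentioned as a restart condition |
| Laboratory values back at baseline | yes | not mentioned as a restart condition |
| Subject amenable to close follow-up | yes | not mentioned |
| Medical Monitor consulted | not mentioned for this bullet | yes |

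Four conditions stand in one place and one in the other, with no overlap.

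**Step 2: direction of the references.** Section 6.19 cites 6.24 for the DILI criteria and 6.24.3 for the recurrence definition. Sections 6.24.1 to 6.24.3 do not cite 6.19. Section 6.22 cites 6.24 only. A reader who starts at 6.19 is therefore led to 6.24, but a reader who starts at 6.22 or 6.24 is not led to 6.19.

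**Step 3: which event triggers 6.19.** Sections 6.24.1 and 6.24.2 each contain three tiers:
- an elevation that calls for repeat testing;
- a persistent elevation that calls for close observation, with stopping to be considered;
- a list of situations in which study drug is stopped.

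No tier is labelled as the DILI criteria. The restart sentence comes after all three, so it could apply to discretionary stops, to the listed stops, or to both.

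**Step 4: the recurrence definition.** The chain runs 6.23 → 6.19 → 6.24.3. Section 6.23 sends the reader to 6.19, which holds no definition and sends the reader to 6.24.3. Section 6.24.3 lists history-taking, exclusion of other causes, additional tests and the frequency of repeat testing. It gives no threshold and does not define a recurrent elevation. Three sections are linked and none contains the definition.

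**Step 5: could 6.24.1 or 6.24.2 supply it?** Their thresholds are in ALT and total bilirubin, for example ALT above 8 × ULN from a normal baseline, or above 5 × baseline or 400 U/L from a raised one. They govern a first event, give no value specific to AST, and are far from an elevation that counts even when slight. They are also not the section that 6.19 cites.

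**Step 6: retest windows.** 48 / 24 = 2 days and 72 / 24 = 3 days. The Cohort C window of 2 to 3 days lies inside the window of 2 to 5 days.

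**The case against.** The strongest reply is that the two restart texts can both be met. The wording in 6.24 is permissive: it names a consultation and does not say that this suffices or that 6.19 is waived. A site that consults the Medical Monitor and also obtains the DMC conclusion satisfies both sections. Section 7.11 has the DMC receive reports of potential DILI, and 7.12 foresees possible adjudication after DMC review, so the committee is not absent from the process. This stands, and it rules out calling the texts a flat contradiction. It does not supply the missing direction: neither 7.11 nor 7.12 states a restart rule, and a site sent to 6.24 still finds no pointer to 6.19.

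It can also be said that 6.24 might intend its restart sentence only for discretionary stops. That is possible. But the text does not say so, which is the labelling gap in Step 3.

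A reader might infer four stronger points that the documents do not support:
- **That the sections are unconnected.** Section 6.19 cites 6.24 and 6.24.3 by number; only the return reference is missing.
- **That the DMC route uses unblinded data and the Medical Monitor route does not.** Section 5.1 blinds the sponsor and its designees, but no passage states what the DMC sees, and 7.11 leaves its conduct to a charter.
- **That the retest windows contradict each other.** One lies inside the other, so a raised-baseline Cohort C subject retested at 48 to 72 hours meets 6.24.2. Section 6.24.3 also sets a 72-hour limit, for all subjects, on the close-observation steps once DILI is suspected.
- **That Section 6.24 has no thresholds.** It has thresholds for first events; what is missing is the recurrence definition at the place cited.

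**Conclusion.** The point holds as a cross-referencing and definition defect in safety-critical text. Section 6.19 makes restart after a DILI stop conditional on a DMC conclusion and three further conditions. Sections 6.24.1 and 6.24.2, where 6.22 sends the reader, give one consultation step and no pointer to those conditions. They also leave unlabelled which of their tiers bring 6.19 into play. A site following 6.24 as directed could re-expose a subject without the DMC step. The permanent-stop rule rests on a definition that is absent from both sections cited for it.

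In size, this is four restart conditions against one with no return reference, and a chain of three sections that ends without a definition. The Cohort C retest window is a minor matter: a difference between baseline groups that the protocol does not explain. No analysis or sample-size figure depends on any of this.

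The conclusion assumes that at least some subjects stopped under 6.24 are those 6.19 has in mind, which the citation in 6.19 makes hard to doubt. It takes no position on which restart or stopping rule is clinically right.

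**What to change.** Reconcile Sections 6.19, 6.23 and 6.24.1 to 6.24.3:

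- State one restart route for a subject stopped for DILI. Cross-reference it from 6.19 to 6.24 and from 6.24 back to 6.19, so that a reader arriving from 6.22 also finds it.
- State which tiers of 6.24.1 and 6.24.2 are the DILI criteria that 6.19 invokes.
- Put the definition of recurrent elevation in one place, covering bilirubin, ALT and AST and both baseline groups, and correct the references in 6.19 and 6.23 to point to it.
- As a minor clarification, say whether the 48 to 72 hour Cohort C retest window in 6.24.1 also applies under 6.24.2.

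The sponsor's clinical team decides the content of each rule. The cost is protocol wording: the reconciliation itself adds no assessment, visit or analysis.
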